## 9.7. Clinical Laboratory Evaluations

The following clinical laboratory tests will be performed:

- Hematology variables include red blood cell count, hemoglobin, hematocrit, platelet count, white blood cell count with 5-part differential, including ANC and reticulocyte count, and peripheral blood blasts.
- Serum chemistry variables include sodium, potassium, bicarbonate, chloride, magnesium, calcium, phosphorus, albumin, glucose, serum creatinine, uric acid, total protein, blood urea nitrogen, AST, ALT, alkaline phosphatase, lactate dehydrogenase, total and direct bilirubin, and lipid profile (triglycerides and cholesterol).
- Urinalysis variables include protein, glucose, and blood, microscopy assessments, and specific gravity.
- Coagulation: INR, prothrombin time, and aPTT.
- Serum or urine beta-human chorionic gonadotropin ( $\beta$ -HCG) pregnancy test (see Schedule of Events in Section 17.8).

All clinical laboratory values must be appraised by the Investigator as to clinical significance. All abnormal clinical laboratory values considered clinically significant by the Investigator must be recorded on the AE page of the eCRF. Abnormal clinical laboratory values (NCI-CTCAE Grade 3 or 4) occurring during the clinical study will be followed until repeat test results return to normal (or baseline), stabilize, or are no longer clinically significant.

## 9.8. Vital Signs

Vital sign measurements will include systolic blood pressure, diastolic blood pressure, respiratory rate, pulse rate, and body temperature.

## **9.9.      *Electrocardiograms***

Standard supine 12-lead ECGs will be performed by qualified technicians in triplicate (5 minutes apart) as noted in the Schedule of Events. Electrocardiograms will be reviewed at the site for treatment of any urgent issues. The clinical significance of any ECG change must be assessed by the Investigator in the context of the subject's medical history, physical examination, and concomitant medications. The Investigator or delegated physician will review, sign, and date all ECGs.

Whenever there are time matched ECGs and PK sampling, ECGs should be done first. PK samples should be collected within 15 minutes of ECG collection.

## **9.10.     *Physical Findings***

Physical examinations will evaluate the following body systems/organs: general appearance; dermatological; head and eyes; ears, nose, mouth, and throat; pulmonary; cardiovascular; abdominal; genitourinary (optional); lymphatic; musculoskeletal/extremities; and neurological. Weight and height will be recorded in kilograms and centimeters, respectively.

## **9.11.     *Other Safety Assessments***

Not applicable.

## **10. OTHER ASSESSMENTS**

Not applicable.

## **11. STATISTICAL METHODS**

### **11.1. Analysis Sets**

#### **11.1.1. Enrolled Analysis Set**

The Enrolled Analysis Set will include all subjects who signed an ICF and were enrolled in either the Dose Escalation part or Dose Expansion part of the study.

#### **11.1.2. Safety Analysis Set**

The Safety Analysis Set will include all subjects enrolled who received any amount of DS-3201b. Subjects will be summarized according to dose of DS-3201b received.

Four groups of subjects will be identified within the Safety Analysis Set: (1) subjects in the Dose Escalation part, (2) subjects in the Dose Expansion part, (3) subjects treated at the dose level of RDE, and (4) all subjects in the study.

#### **11.1.3. Full Analysis Set**

The Full Analysis Set will include all subjects enrolled in the Dose Escalation part or the Dose Expansion part who received any amount of DS-3201b and who had at least 1 post-baseline bone marrow assessment.

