- Duration of response (DOR): Time from the first objective evidence of response to the first objective evidence of disease progression
- Overall survival (OS): Time from the date of enrollment to the date of death from any cause
- 30- and 60-day mortality rate

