## **11.2. General Statistical Considerations**

The primary analysis is to assess the safety and tolerability of DS-3201b in subjects with relapsed or refractory AML or ALL and to determine the RDE or establish the safety and tolerability of DS-3201b at the RDE.

The primary analysis will occur after all subjects in Part 2 have either discontinued the study or have completed at least 6 months of treatment. After the primary analysis, the main study will be closed. Subjects in Part 1 and Part 2 who are still on study at least 6 months after enrollment

of the last subject in the study may be eligible to continue receiving study drug in a separate extension phase of the protocol (see Section 17.9). Data collected from those subjects may be captured in a separate database.

Descriptive statistics will be provided for selected demographic, safety, efficacy, and PK parameters as well as plasma DS-3201a concentrations, and will be summarized by dose level/study day/time points, as appropriate. Descriptive statistics on continuous variables will include means, medians, standard deviations, minimum, and maximum (as well as geometric means and geometric coefficient of variation for Cmax and AUC PK parameters), while categorical data will be summarized using frequency counts and percentages. Graphical summaries of the data may be presented.

The last non-missing value of a variable taken before the first dose of study drug will be used as the baseline value, unless otherwise specified. Assessments of change from baseline to post-treatment or the ratio of post-treatment to baseline will include only those subjects with both baseline and post-treatment measurements. In general, missing or dropout data will not be imputed for the purpose of data analysis, unless otherwise specified.

Safety analyses will be performed based on the Safety Analysis Set. Analysis of PK parameters will be based on the PK Analysis Set and biomarker analyses will be based on the PDy Biomarker Analysis Set. Efficacy endpoints will be analyzed based on the Full Analysis Set. Data from the Dose Escalation part will be summarized by dose level and overall.

A detailed SAP describing the methodology to be used in the final analysis will be prepared and finalized before database lock. Statistical methods described within this document may be changed based on advances in research.

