### **11.4. Efficacy Analyses**

Response to treatment will be evaluated using the revised IWG response criteria for AML or the NCCN response criteria 2016 for ALL, respectively (Section 17.3). The efficacy endpoints will

be CRc rate (including CR, CRi, and CRp), MLFS, PR rate, ORR, DOR, OS, and 30- and 60-day mortality rate for AML and ALL, respectively.

For the binary efficacy endpoints, the point estimate and exact 95% confidence interval will be provided. Time-to-event variables, such as DOR and OS, will be analyzed using the Kaplan-Meier method by dose level and overall.

The best overall response will be determined for each subject, in the order of CR, CRp or CRi, PR, and treatment failure (TF). For each category as well as response (CRc or PR), the point estimate and 95% confidence interval will be calculated for the proportion.

OS is the time from the first dose of DS-3201b to the death. The censoring rules will be specified in the SAP.

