## 11.10. Sample Size Determination

The Dose Escalation part of the study will enroll 3 to 6 subjects in each cohort, based on a BLRM under the EWOC principle. It is possible that a dose level may enroll more than one cohort based on the BLRM recommendation. The number of subjects enrolled depends on the observed DLTs, but it is expected that 21 or more subjects might be enrolled in the Dose Escalation part.

For the Dose Expansion part, additional subjects will be enrolled at the RDE dose level as suggested based on data in the Dose Escalation part. Approximately 20 subjects each with AML and ALL will be enrolled at the RDE dose level, including those dosed at the same dose level in the Dose Escalation part, which is expected to number between 6 and 9. The size of 40 is deemed to be sufficient for the assessment of safety and tolerability, as well as the clinical antitumor activity. Assuming a true CRc rate of 20%, the probability of observing 3 or more CRc among the 20 subjects is 79.4% for AML and ALL, respectively.

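### Overall survival, early mortality and response rates are analysed only in treated subjects who had a post-baseline marrow, so those who die or leave before one drop out of the denominator

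*Combined protocol and SAP*

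**What the plan says.** Section 11.1.3 restricts the Full Analysis Set (FAS) to enrolled subjects "who received any amount of DS-3201b and who had at least 1 post-baseline bone marrow assessment". Section 11.2 then states: "Efficacy endpoints will be analyzed based on the Full Analysis Set". Section 11.4 lists the efficacy endpoints as the composite complete remission (CRc) rate followed by "MLFS, PR rate, ORR, DOR, OS, and 30- and 60-day mortality rate for AML and ALL, respectively". No endpoint is exempted.

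The survival clock starts before any post-baseline marrow. In Section 11.4, "OS is the time from the first dose of DS-3201b to the death"; in Section 3.1.3 the origin is enrollment instead ("Overall survival (OS): Time from the date of enrollment to the date of death from any cause"), and Section 7 agrees with Section 3.1.3.

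A set without the marrow condition already exists: "The Safety Analysis Set will include all subjects enrolled who received any amount of DS-3201b" (Section 11.1.2). Section 11.2 assigns it to safety analyses only.

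Three other places bear on response:

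- Section 11.4 ranks best response for every subject, ending in treatment failure (TF).
- The AML table in Section 17.3.1 counts as TF a subject who dies before response is assessed, whose leukemia persists in blood or marrow, or who reaches no remission.
- The sample-size argument in Section 11.10 works with "the probability of observing 3 or more CRc among the 20 subjects is 79.4"%, with no marrow condition on the 20.

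**The concern.** Entry to the FAS depends on something that happens after treatment starts: the subject must live long enough, and attend, to have a marrow taken. OS and early mortality are measured from before that point and need no marrow, so the condition selects on the outcome. A subject who dies on Day 5 without a marrow counts in neither OS nor 30-day mortality.

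For response, a subject with no post-baseline marrow cannot be a documented CRc or PR. Removing such subjects can only raise CRc and ORR. In AML it also removes subjects whom Section 17.3.1 calls failures.

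For mortality the direction is not fixed. Dropping early deaths lowers it and flatters OS; dropping survivors who left without a marrow raises it. A reader could not tell which had happened without the reasons for exclusion and the vital status of those excluded.

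At stake are ORR and OS, which are Part 2 secondary objectives (Section 2.1.2.2), and response in Part 1, which is exploratory (Section 2.1.3.1).

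**Working it through.** **1. The plan's own figure.** Inputs from Section 11.10: n = 20 per disease, true CRc rate 20%, at least 3 CRc.

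P(X ≥ 3) = 1 − [0.8^20 + 20 × 0.2 × 0.8^19 + 190 × 0.2² × 0.8^18] = 1 − [0.0115 + 0.0576 + 0.1369] = 0.794.

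The stated 79.4% is reproduced. It takes all 20 subjects as the denominator.

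**2. Who can be lost.** The first scheduled post-baseline marrow is Cycle 1 Day 8 ± 2 days (Sections 6.3.1.3, 6.3.2.4 and 7). A subject who has it enters the FAS. Response assessment also continues after drug is stopped, until progression or new therapy (Section 4.2.1.1), and unscheduled marrows are recorded (Section 17.8 footnotes). Those lost are therefore mainly subjects who die or leave before about Day 6 to 10, or who miss the Day 8 marrow and never have a later one. Section 3.1.4 makes the second route possible: subjects below CR with more than 5% circulating blasts need later marrows only if clinically indicated.

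**3. Early deaths, as an illustration.** The protocol gives no count. Assume exponential survival. Section 1.2 gives a 3.8-month median for refractory AML and says survival in relapsed AML is under 6 months. It does not call the latter a median, so 6 months is used here as an assumed upper value. Section 1.2 gives no ALL figure.

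P(death by day d) = 1 − exp(−ln 2 × d / (median × 30.44))

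| Assumed median | By Day 8 | Of 20 | Day 6 to Day 10 | By Day 29 (Day 8 marrow missed) |
|---|---|---|---|---|
| 3.8 months | 4.7% | 0.94 | 3.5% to 5.8% | 16.0% |
| 6 months | 3.0% | 0.60 | 2.3% to 3.7% | 10.4% |

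The 3-month life-expectancy criterion (Section 4.1.1) should lower these.

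Under the 3.8-month assumption, 30-day mortality is 16.5% in all treated subjects and 12.4% in those who must survive to a Day 8 marrow. The 60-day figures are 30.2% and 26.8%.

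**4. Effect on the reported rates.** Twenty treated, Clopper-Pearson 95% intervals. The event counts are assumed: 4 CRc, and 3 deaths by Day 30.

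| Subjects without a marrow | CRc | 30-day mortality |
|---|---|---|
| None | 4/20 = 20.0% (5.7 to 43.7) | 3/20 = 15.0% (3.2 to 37.9) |
| One, died | 4/19 = 21.1% (6.1 to 45.6) | 2/19 = 10.5% (1.3 to 33.1) |
| One, alive | 4/19 = 21.1% (6.1 to 45.6) | 3/19 = 15.8% (3.4 to 39.6) |
| Two, both died | 4/18 = 22.2% (6.4 to 47.6) | 1/18 = 5.6% (0.1 to 27.3) |
| Two, both alive | 4/18 = 22.2% (6.4 to 47.6) | 3/18 = 16.7% (3.6 to 41.4) |
| Two, one of each | 4/18 = 22.2% (6.4 to 47.6) | 2/18 = 11.1% (1.4 to 34.7) |

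**5. A threshold that depends on the denominator.** Section 3.1.8 applies a 10% ORR limit in Part 2 after 10 subjects are enrolled and names no analysis set. One response in 11 treated is 1/11 = 9.1%. If one of the 11 has no marrow, the FAS gives 1/10 = 10.0%, on the other side of the limit.

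**The case against.** Five points can be made for the plan.

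- **The loss would be visible.** Section 11.3 requires baseline tables for the Enrolled, Full and Safety sets, so the number excluded can be found by subtraction. Section 9.1 requires the cause of every death in the reporting period to be recorded as an SAE, and Section 11.6.1 lists deaths. This stands, but none of it yields an OS, mortality or response estimate in all treated subjects, or the reasons for exclusion from the FAS.
- **Best response for every subject can be read as every FAS subject.** A subject with a Day 8 marrow who dies before Cycle 2 Day 1 can be in the FAS and be TF. This also stands. The mismatch with Section 17.3.1 is confined to AML subjects with no post-baseline marrow at all.
- **A response-evaluable set is a defensible choice in a descriptive Phase 1 trial.** The ALL table (Section 17.3.2) calls failure to reach CR refractory disease but does not address a missing marrow. For ALL response, the alternative is therefore a choice to be stated, not the cure of a contradiction. The argument gives no reason to require a marrow for OS or mortality.
- **The effect is small.** Every illustrated rate lies inside the all-treated interval. The fall to 5.6% needs two of three early deaths to have no marrow, against fewer than one expected death by Day 8. This stands and limits the severity.
- **The SAP may settle it.** Section 11.2 announces a separate SAP, and Section 11.4 leaves OS censoring to it. That text was not supplied, so the conclusion concerns the protocol wording.

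**Conclusion.** The concern holds. Followed as written, Sections 11.1.3, 11.2 and 11.4 remove treated subjects from OS and early-mortality estimates for lack of a test those endpoints do not use. They also remove from the AML response rate some subjects whom the protocol's own criteria class as failures.

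The probable size is modest: about one subject or fewer in 20 lost through death by Day 8, if survival is exponential with a median of 3.8 to 6 months and the Day 8 marrow is otherwise done. More would be lost if that marrow is often missed. Early mortality is the more sensitive estimate, because a single subject is a large share of a small number of deaths. If every treated subject has a marrow, nothing changes.

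The primary safety and MTD/RDE conclusions do not depend on this set. The point should be fixed before the analysis, but it does not threaten the trial's main purpose.

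**What to change.** Amend Section 11 and carry the same wording into the SAP:

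1. Analyse OS and 30- and 60-day mortality in all treated subjects, using the Section 11.1.2 definition. Settle the OS origin at the same time, since Sections 3.1.3 and 7 differ from Section 11.4.
2. Use the same set for the main CRc and ORR analyses. Count treated subjects with no post-baseline marrow as non-responders. For AML this follows the TF row of Section 17.3.1; for ALL it must be stated explicitly.
3. Keep the present FAS, renamed as response-evaluable, for a sensitivity analysis of response only.
4. Report the number outside that set, separately for AML and ALL, with reasons and vital status.
5. State which denominator the ORR check in Section 3.1.8 uses.

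No new data or visits are needed. The cost is that response rates may be slightly less favourable, and some subjects will be classed as non-responders without a marrow result.

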#### **11.1.4. Dose-Limiting Toxicity Evaluable Set**

The DLT-evaluable Set will include all subjects enrolled in the Dose Escalation part who had a DLT within the first cycle (28 days) on study, or without DLT but received at least 75% of scheduled DS-3201b doses during the DLT evaluation period.

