#### 3.1.2.1. Part 1 (Dose Escalation)

Dose escalation of DS-3201b to determine the MTD will be guided by a Bayesian logistic regression model (BLRM), following the escalation with overdose control (EWOC) principle. The logistic regression model for the DLT rate will include 2 parameters: the intercept and the slope. After the first 3 subjects of each cohort complete the DLT evaluation during Cycle 1 (see Section 3.1.7.2), the posterior distributions of the DLT rate will be derived for all provisional dose levels based on the BLRM using the DLT outcome data from all assessed doses and a pre-specified prior distribution for the model parameters. The posterior probability of the DLT rate in the following 4 intervals at each dose level ([0%, 16%) as the DLT rate interval for under-dosing, [16%, 33%) as the target DLT rate interval, [33%, 60%) as the DLT rate interval for excessive toxicity, and [60%, 100%) as the DLT rate interval for unacceptable toxicity) will then be calculated and used for dose recommendation for the next cohort according to the EWOC principle.

The EWOC principle requires that the BLRM recommended dose for the next cohort of subjects is defined as the highest posterior probability of the DLT rate in the target DLT rate interval [16%, 33%) among all dose levels fulfilling the overdose control constraint: there is less than a 25% probability for the DLT rate  $>33\%$  (probability for excessive or unacceptable toxicity). The dose increment will be as follows:

- The dose level increment should be no less than 30% in order to have distinction among dose levels considering the inter-subject variability in exposure, but flexibility may be applied in selecting the dose to accommodate the available dosage form strengths.
- The dose level increment should be no more than 100% even if the model suggests a higher dose than 100% for the next cohort.

Cohorts of 3 to 6 subjects will be enrolled and assessed for DLT before escalation to a new higher dose. In the event of a DLT, the next 2 subjects will receive DS-3201b treatment starting

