at least 1 week apart. As an exception, the model will be reevaluated before enrollment of any additional subjects to the cohort if 2 evaluable subjects experience DLT before the enrollment of the next subject after the BLRM dose recommendation. The dose for the next cohort will be chosen by the Sponsor and Principal Investigators based on the dose recommendation by the BLRM, clinical assessment of toxicity profiles and efficacy, and PK/PDy information observed thus far.

Based on the safety results available so far from the Phase 1 study of DS-3201 currently ongoing in Japan (DS3201-A-J101), escalation from the starting dose of 100 mg to the second dose level will be by less than 100%.

Enrollment of subjects to a new cohort requires completion of a DLT evaluation of at least 3 subjects treated in the current cohort. Subjects who have neither completed a DLT evaluation nor experienced a DLT will not be included in the BLRM update. In the event that subjects in the previous cohort experience a DLT after the enrollment of subjects to a new cohort has begun, dose level assignment of the next subject in the new cohort will be based on an updated BLRM using DLT outcome data from all assessed doses.

For a subject to be considered evaluable for dose escalation decisions, the subject must have received at least 75% of the doses (ie, 21 days) during the DLT evaluation period or experienced a DLT in Cycle 1. The final MTD will be decided based on considerations of the respective MTD estimated by the BLRM, and on an overall assessment of safety data from subsequent cycles and of PK/PDy response collected at all different doses tested. For dose determination, the following stopping rules will be implemented for the Dose Escalation part: (a) at least 6 evaluable subjects at the MTD level with at least 21 evaluable subjects in total enrolled in the Dose Escalation part, (b) at least 9 evaluable subjects have been enrolled at a dose level which is the model's recommendation for the next dose cohort and for which the posterior probability of targeted toxicity is at least 50%, or (c) dose level 1 is too toxic.

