#### **3.1.7.2. Dose-limiting Toxicities**

Dose-limiting toxicity is defined as a clinically significant non-hematologic TEAE or abnormal clinical laboratory value that is clearly not related to disease progression, intercurrent illness, and occurring during the first cycle (28 days) on study that meets any of the following criteria:

- National Cancer Institute (NCI) – Common Terminology Criteria for Adverse Events (CTCAE), Version 4 Grade 3 aspartate aminotransferase (AST) (SGOT), alanine aminotransferase (ALT) (SGPT), or bilirubin for  $\geq 7$  days.
- NCI-CTCAE Grade 4 AST (SGOT) or ALT (SGPT) of any duration.
- All Grade 4 non-hematologic toxicities of any duration.
- Any Grade 5 toxicity, unless proven to be clearly and incontrovertibly related to disease progression or intercurrent illness will constitute a DLT.
- All other clinically significant, non-hematological NCI-CTCAE Grade 3/4 AEs.

Exceptions are as follows:

- Grade 3 or 4 nausea, vomiting, and diarrhea that do not require hospitalization or total parenteral nutrition (TPN) support and can be managed with supportive care to  $\leq$ Grade 2 within 48 hours.
- Alopecia and study drug-related fever will not constitute DLT.
- Grade 3 or 4 electrolyte abnormalities that are corrected to  $\leq$ Grade 2 within 24 hours.
- Grade 3 or 4 differentiation syndrome which improves to  $\leq$  Grade 1 within 7 days of the start date of  $\geq$  Grade 3 differentiation syndrome and which is not associated with end-organ damage.

Myelosuppression and associated complications are expected events during leukemia therapy. Only prolonged myelosuppression, as defined by absolute neutrophil count (ANC)  $<0.5 \times 10^9/L$ , platelets  $<20 \times 10^9/L$ , and marrow cellularity  $<5\%$  on Day 42 or later (6 weeks) from start of therapy without any evidence of leukemia will be considered in defining the MTD and DLT. DLT evaluation of myelosuppression will be decided between the Investigators and Sponsor Medical Monitor during safety review meetings.

Subjects who are unable to complete at least 75% of the prescribed dose (ie, 21 days) of DS-3201b during the DLT evaluation period as a result of non-disease-related  $\geq$ Grade 2 AEs will be considered to have a DLT.

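### A myelosuppression DLT can only be established from Day 42, but the DLT-evaluable set, the evaluability rule and the model run are tied to the 28-day first cycle, and no model re-run is required after the last cohort

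*Combined protocol and SAP*

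**What the plan says.** **DLT definition (protocol 3.1.7.2).** The general definition covers events "occurring during the first cycle (28 days) on study that meets any of the following criteria". A separate paragraph deals with marrow toxicity. Only ANC below 0.5 × 10⁹/L, platelets below 20 × 10⁹/L and marrow cellularity under 5% "on Day 42 or later (6 weeks) from start of therapy without any evidence of leukemia will be considered in defining the MTD" and the DLT. It adds: "DLT evaluation of myelosuppression will be decided between the Investigators and Sponsor Medical Monitor during safety review meetings".

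**Evaluability and model run (3.1.2.1).** The Bayesian logistic regression model (BLRM) is run "After the first 3 subjects of each cohort complete the DLT evaluation during Cycle 1"; 11.11.3 repeats this. A subject is evaluable for escalation if he or she "received at least 75% of the doses (ie, 21 days) during the DLT evaluation period or experienced a DLT in Cycle 1". On gating: "Enrollment of subjects to a new cohort requires completion of a DLT evaluation of at least 3 subjects treated in the current cohort". On exclusions: "Subjects who have neither completed a DLT evaluation nor experienced a DLT will not be included in the BLRM update". If a subject in the previous cohort has a DLT after a new cohort has begun enrolling, the next assignment uses an updated BLRM.

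**Analysis set (11.1.4).** The DLT-evaluable set takes Dose Escalation subjects "who had a DLT within the first cycle (28 days) on study, or without DLT but received at least 75% of scheduled DS-3201b doses".

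**Reporting (11.6).** There are two DLT outputs. One is a by-dose incidence table with no stated restriction; the other is a summary confined to the DLT-evaluable set. Under 11.2 the default population for safety is the Safety Analysis Set.

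**Declaring the MTD (3.1.7.1, 3.1.8).** Stopping rule (a) needs 21 evaluable subjects in total, 6 of them at the MTD level. The estimated MTD must have P(DLT rate >33%) below 25% and a posterior mean of at most 25%. The final MTD also weighs safety data from later cycles.

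**Schedule (17.8, footnote a).** The cohort DLT assessment takes place after Day 28.

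**The concern.** The protocol defines a DLT that cannot be established until 14 days after the window in which DLTs are counted. A subject who has taken at least 75% of Cycle 1 doses and is aplastic at Day 28 has, on that day, no DLT, and can be counted as a clean evaluable subject. If the Day-42 criterion is then met, 11.1.4 does not say what to do with the event.

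Determining the MTD is a primary objective of Part 1 (2.1.1.1). Two things are at stake:

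- The next cohort may open between Day 28 and Day 42, and its second and third subjects may start one day after the first (3.1.2).
- After the last cohort, the stopping rules and the MTD estimate may rest on a model that does not contain the event.

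Subjects whose dosing falls below 75% because of non-disease-related adverse events of Grade 2 or higher are not affected, since 3.1.7.2 already makes them DLTs.

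**Working it through.** **1. Timing.** 42 − 28 = 14 days. A DLT under the myelosuppression criterion can therefore never satisfy the first branch of 11.1.4, nor the Cycle 1 DLT condition in 3.1.2.1.

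**2. The second branch of 11.1.4, for a subject with at least 75% of doses.**

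- If without DLT means none at any time, the subject is in neither branch and is excluded.
- If it means none in Cycle 1, the subject is in the set, and nothing says whether the later event is coded as a DLT.

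On either reading the set-restricted summary in 11.6 may omit the event, or disagree with the unrestricted incidence table in the same section.

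**3. Is there a hold at Day 28?** The three-evaluation gate could act as one, but 3.1.2.1 places completion of the evaluation in Cycle 1. The safety review meetings (3.1.7.2) and the pre-escalation review (11.8) give no date. No hold is stated.

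**4. Is a re-run required?** Only once a new cohort is enrolling. After the last cohort that trigger cannot occur.

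**5. Can one event change the dose?** The plan gives no figure for this, so the following are constructed histories, not trial data. Inputs from 11.11: logit π(d) = log α + β log(d/700); (log α, log β) bivariate normal with means (−1.005, −0.093), SDs (1.289, 1.098) and correlation −0.182; doses 100, 150, 250, 350, 500, 700 and 1000 mg. The recommended dose has the highest P(16% ≤ π < 33%) among doses with P(π ≥ 33%) < 25%. The MTD estimate also needs a posterior mean of at most 25%. Posteriors are by numerical quadrature split at the 16% and 33% limits.

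| History (3 subjects per lower dose) | Event not counted | Event counted | Dose |
|---|---|---|---|
| Non-final: 0/3 at 100–350 mg; 500 mg 0/3 vs 1/3 | P(≥33%) at 700 mg 10.2% | 27.1% | recommended 700 → 500 mg |
| Non-final: 0/3 at 100–500 mg; 700 mg 0/6 vs 1/6 | P(≥33%) at 1000 mg 19.9% | 38.1% | recommended 1000 → 700 mg |
| Last: 1/3 at 350 mg, 0/3 at other lower doses; 700 mg 1/6 vs 2/6 | at 700 mg: P 9.7%, mean 19.2% | P 25.6%, mean 26.15% | MTD 700 → 500 mg |
| Last: 0/3 at 100–500 mg; 700 mg 2/6 vs 3/6 | at 700 mg: P 18.6%, mean 22.8% | P 42.4%, mean 31.7% | MTD 700 → 500 mg |
| Last: 0/3 at 100–500 mg; 700 mg 1/6 vs 2/6 | at 700 mg: P 5.3%, mean 15.1% | P 18.6%, mean 22.8% | 700 mg, no change |

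The last-cohort histories obey the overdose rule at each step. In the third row, 1/3 at 350 mg leads to 500 mg (P 15.1% there, 33.3% at 700 mg). Then 0/3 at 500 mg leads to 700 mg (P 19.5%), and 1/3 at 700 mg repeats 700 mg (P 22.9%). In the fourth row, 0/3 at 500 mg leads to 700 mg (P 10.2%), and 1/3 there repeats 700 mg (P 14.8%).

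**6. Stopping rule (a).** In the third and fourth rows, evaluable subjects = 5 × 3 + 6 = 21, with 6 at 700 mg, so the rule is met on Day-28 data. With the event counted, the estimate is 500 mg, which has only 3 evaluable subjects, and the rule is not met. If the subject is instead dropped, 20 are evaluable and the rule is again not met. That helps only if the set is rebuilt after Day 42.

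**7. Spread.** With one cohort of three per dose, four histories reach 700 mg within the overdose rule: no DLT, or one at 150, 250 or 350 mg. After 1/3 at 700 mg and three more subjects, 1/6 versus 2/6 changes the recommendation in three of them (1000 to 700 mg, 1000 to 700 mg, 700 to 500 mg) and not in the no-DLT history. This is an enumeration, not a probability.

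**The case against.** The strongest reply is that myelosuppression has its own route. Section 3.1.7.2 takes it out of the 28-day list and gives it to the investigators and medical monitor. The data will exist: 3.1.4 allows drug to be withheld and the marrow repeated in two weeks, and 6.3.1.7 schedules a marrow at Cycle 2/Day 15 (28 + 15 = Day 43) after aplasia. The model never declares the MTD alone, because later-cycle safety is weighed as well. All of this stands, and it makes a wrong final dose less likely. It does not put the event into the evaluable set, the model or the count for rule (a).

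Several stronger readings are tempting, and the documents do not support them:

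- A reader might infer that the event disappears from 11.6. The unrestricted incidence table could show it, so the risk is omission from one output or disagreement between two.
- A reader might infer that 11.1.4 shuts the subject out. That depends on how without DLT is read.
- A reader might infer that the model closes at Day 28. Footnote a gives a start rather than an end, and the late-DLT clause has no 28-day limit, so for non-final cohorts the effect is mainly delay.
- A reader might take the hypocellular-marrow DLT at 700 mg/day in 1.4.1 as a lost event. It was recorded as a DLT and its onset day is not given. It shows only that marrow toxicity is relevant here.

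**Conclusion.** The point holds and should be fixed. The Day-42 and 28-day rules conflict in the text. For a subject with at least 75% of doses, a marrow DLT cannot be entered in 11.1.4 as a DLT; no Day-28 hold is stated; and no model re-run is required after the last cohort. Confidence in that is high.

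In the two last-cohort histories where one event matters, the MTD estimate is one dose level too high (700 instead of 500 mg). The first is a narrow crossing, 0.6 percentage points over the overdose limit and 1.15 over the mean limit; the second is clear. In a third history nothing changes. These results rest on the prior as printed, three subjects per lower dose, and assumed DLT counts.

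Confidence in the operational effect is moderate. The event needs all three marrow criteria, no leukemia and at least 75% of doses taken, and the documents give no frequency. The Cohort Management Plan cited in 3.1.2.1 and the detailed SAP promised in 11.2 are not available here and could close the gap.

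**What to change.** Keep the 28-day DLT window and extend it to Day 42 for prolonged myelosuppression only, in 3.1.2.1, 3.1.7.2, 11.1.4 and footnote a of the schedule. Then state that:

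- a subject who meets the Day-42 criterion counts as a DLT in the evaluable set, the BLRM and both DLT outputs in 11.6;
- unresolved aplasia at Day 28 is pending, not DLT-free;
- the BLRM is re-run once a pending case resolves, and in any event before stopping rule (a) or (b) is applied and the MTD is declared.

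The cost is wording and one further model run per pending case. An escalation or MTD decision may wait about two weeks for the few subjects with aplasia, for whom a repeat marrow is already provided (3.1.4, 6.3.1.7).
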